#### 4.2.3 Analysis Populations

There are five analysis populations defined as below:

GlaxoSmithKline Consumer Healthcare Confidential Page 12 of 36

211206

Statistical Reporting and Analysis plan Draft V2.0 20JAN2021

| Table 4-1                           | Analysis Population  |  |   |
|-------------------------------------|--|--|---|
| Population                          | Definition / Criteria  | Analyses
Evaluated  | Treatment
s to used
for
Analyses |
| Enrolled                            | Comprise of all the subjects who have signed ICF,
though may or may not be randomized later into the
study.  | Disposition  |   |
| Intent-To-
Treat
(Randomised) | Comprise of all randomized subjects.
This population will be based on the treatment to which
the subject was randomized.
Any subject who receives a treatment randomization
number will be considered to have been randomized.   | Efficacy
Demographics/Di
sposition/Medical
History/Concomit
ant
Mediaction/Comp
liance | Planned
treatment
received          |
| Safety                              | Comprise of all subjects who receive at least one dose
of study treatment.
This population will be based on the treatment the
subject actually received.  | Study Population
Safety   | Actual
treatment
received           |
| Intent-To-
Treat
(Modified)   | Comprise of all randomized subjects who have at least one post baseline POM VAS assessment.  | Efficacy
Demographics   | Planned
treatment
received          |
| Per-Protocol
(PP)                | All subjects from the mITT population who do not have
any major protocol deviations (which are not affecting
primary efficacy endpoint) and also weight
compliance > 65% and application compliance >
80%that could confound the interpretation of the
efficacy analyses.
Protocol deviations that would exclude subjects from
the PP population will be discussed in the BDRM. | Primary Efficacy
Demographics.  | Actual
treatment
received           |

Table 4-1Analysis Population

The numbers of subjects included in each of the analysis populations, and the number excluded from each population broken down by the reason for exclusion will be presented (PPD) using enrolled population. Subjects excluded from any of the analysis populations will be listed in PPD, with the reason for exclusion.

#### 4.3 Subject Demographics and Other Baseline Characteristics

Demographic and baseline characteristics summaries will be produced for the ITT, mITT, PP and SAF.

Page 13 of 36

Statistical Reporting and Analysis plan Draft V2.0 20JAN2021

#### 4.3.1 Demographic Characteristics

Categorical demographic variables include gender (Male, Female), race (American Indian or Alaska Native, Asian, Black or African American, Native Hawaiian or Other Pacific Islander, White). These variables will be summarized by the number and percentage of subjects with each relevant characteristic in each treatment group.

Body Mass Index (BMI) will be calculated as weight  $(kg)/[height (m)]^2$ . Age in years, weight in kg, height in cm and BMI in kg/m^2 will be summarized by the mean, standard deviation, median, minimum and maximum values in each treatment group.

All the demographic related information will be taken from Demographic CRF page. Other baseline characteristics information will be taken from the corresponding CRF page for the baseline visits.

Examination on Ankle sprain will be taken from the Examination of Ankle Sprain/Diagnostic Testing for Ankle CRF page.

All demographic information will also be tabulated for ITT, mITT and SAF populations in **PPD**.

Demographic variables will be listed in PPD us

using ITT population.

#### 4.3.2 General Medical History

Medical diagnoses/surgeries will be listed by subject using ITT population, with date of diagnosis/surgery, and whether or not the diagnosis/surgery was an active problem at the start of study drug administration (**PPD**) (CRF page: Medical History).

The presence/absence of any relevant medical history or current medical conditions will be tabulated.

Medical conditions will also be summarized using ITT population by numbers and percentages of subjects having a condition (**PPD**).

#### 4.3.3 Characteristics of Disease

Baseline disease characteristics will be tabulated from the screening CRF page of Pain on Movement, Tenderness, Ankle Joint Function, Ankle Swelling.

The tables will be provided using ITT population (**PPD**). All information will be listed in the listing (**PPD**).

GlaxoSmithKline Consumer Healthcare Confidential Page 14 of 36

# 4.4 Treatments (Study Drug, Rescue Medication, other Concomitant Therapies, Compliance)

Compliance data will be summarized for the safety population and ITT population. Exposure and other medications will be summarized on the safety population.

#### 4.4.1 Study Drug Compliance and Exposure

#### Compliance:

Compliance will be summarized descriptively based on the following points in PPD using ITT and Safety population respetively, PPD by ITT population on the following three :

- 1. % of scheduled applications made
- 2. % of gel used relative to number of actual applications \* 2g, and
- 3. compliance category (Good/Moderate/Poor).
- 1. % of scheduled applications made will be calculated in following way
  - a. % of scheduled applications compliance per tube:
  - Total number of applications made: Compliance will be summerized based on the percent of scheduled application made. Percent of scheduled application made for each dosing time morning, noon, late afternoon and late evening respectively will be calculated in the following manner.
  - If replacement kit number and replacement date (CRF: Study Medication Replacement) are missing -
    - $\circ$  Expected number of application from tube k=(number of applications per day from tube k) \* duration of days in the study ; where, k=1,2,3,4
    - Actual number of application from tube k= (Expected number of application)
       –[sum of (number of missed applications per day from tube k)\* duration of
       days gel is applied i.e. (Day i Day 1)]; where, i=1,2,3,4,5,6,7,8; k=1,2,3,4
    - Percent of scheduled application made from tube k= (Actual number of application from tube k ( where k=1 to 4) / Expected number of application from tube k) \*100.

GlaxoSmithKline Consumer Healthcare Confidential

Page 15 of 36

- If replacement kit number and replacement date (CRF: Study Medication Replacement) are non-missing then
  - Expected number of application from tube k=Sum of [ (number of applications per day from tube k from kit no. x) +(number of applications per day from tube k from kit no. y)\* duration of days in the study]; where x= Old kit # and y= New kit #, k=1,2,3,4
  - Actual number of application from tube k= (Expected number of application from tube k from kit no. x) –[sum of (number of missed applications per day from tube k from kit x)+ sum of (number of missed applications per day from tube k from kit y)]\* duration of days gel is applied i.e. (Day i Day 1)]; where, i=1,2,3,4,5,6,7,8; k=1,2,3,4; x= Old kit # and y= New kit #
- Percent of scheduled application made from tube k= (Actual number of application from tube k ( where k= 1 to 4) / Expected number of application from tube k) \*100% of scheduled applications compliance overall:
  - Over all Compliance % = [sum of (actual # of application from each tube)/sum of (expected # of application from each tube)\*100]

Scheduled applications will include all scheduled applications through the day before the final visit. On day 1, the percentage of gel used will be calculated based on the possible number of administrations on that day. If only 3 were possible, then 100 % compliance on that day will be considered 3 applications.

- % of gel used relative to number of actual applications \* 2g will be derived as following -
  - Total weight of study medication used: The percent (%) of gel used will be computed relative to the actual number of application made from randomization through the final visit multiplied by 2 g.in two ways –
  - If replacement kit number and replacement date (CRF: Study Medication Replacement) are missing then
  - Expected weight of study medication used from tube k= (number of applications per day from tube k )\*2g \* Expected number of days gel to be applied from tube k
  - Actual weight of study medication used from tube k= [(Baseline weight of tube k (weight of tube k after last day of application ; k=1, 2, 3, 4

GlaxoSmithKline Consumer Healthcare Confidential Page 16 of 36

**Percent of total medication used** = (Actual weight of medication used/Expected weight of medication used)\*100

In case there is repeated usage of single tube in a day then the over usage of the medication will be reflected in weight compliance.

- Compliance category: Compliance category will be defined in the following way -
  - Good: > 80% of the gel has been applied and > 80% of scheduled applications made,
  - Moderate: not Good and not Poor
  - Poor: < 50% of the gel has been applied or < 50% of scheduled applications made.

For subjects applying active gel only twice per day (DDEA 2.32%), an additional compliance computation will be performed relative to the tubes and applications of active gel. If a subject is falls into good compliance category in both (separately for the active gel and also combined with placebo) then that subject will be included in the PP protocol population.

For each subjects time of the first application, application of the study drug each time point each day and the weight of the four tubes on Day 1, 3, 5 and 8 will be listed in **PPD** :

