## 4.2.2 Protocol Deviations

Protocol deviations will be tracked by the study team throughout the conduct of the study. Data will be reviewed during Blinded Data Review Meeting (BDRM) prior to database lock to ensure all important deviations are captured and categorised.

Protocol deviations that would exclude subjects from PP population may include (but are not limited to) the following:

- Subjects failing to meet inclusion and exclusion criteria but are included in the study
- Subjects without a Day 5 POM VAS assessment
- Subjects with get application compliance <=80% or weight compliance <=65% or weight compliance >=143% or application compliance >=143% with study treatment.
- Subjects taking prohibited medication (Refer Appendix 4)
- Subjects identified with other major protocol deviations

GlaxoSmithKline Consumer Healthcare Confidential

Page 11 of 36

Full details of the major and minor protocol deviations are provided in Appendix 3.

The number and percentage of subjects with any major protocol deviations and with each type of major protocol deviations will be presented by treatment group (PPD ) using ITT population and listed in PPD . Any minor protocol deviations will also be listed similarly PPD .

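### SAP 4.4.1 counts the replacement kit in expected but not in actual applications, so a fully adherent subject whose kit was replaced can miss the 80% per-protocol cut-off

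*SAP*

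**What the plan says.** SAP 4.4.1 has two branches for application compliance, according to whether the CRF records a replacement kit. When it does, the expected count takes in the old kit x, "Expected number of application from tube k=Sum of [ (number of applications per day from tube k from kit no. x", and the new kit, "number of applications per day from tube k from kit no. y", with a multiplication by days in the study. The actual count begins with "Actual number of application from tube k= (Expected number of application from tube k from kit no. x" and no matching kit y term. What is subtracted nevertheless includes the new kit: "sum of (number of missed applications per day from tube k from kit y". The percentage is the ratio of the two: "Percent of scheduled application made from tube k= (Actual number of application from tube k", divided by the expected number. The overall percentage sums the same per-tube counts.

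For gel weight, the same section announces a computation "through the final visit multiplied by 2 g.in two ways". In the text as available, only the case without a replacement kit follows.

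SAP 4.2.2 lists as a reason for exclusion from the PP set: "Subjects with get application compliance <=80% or weight compliance <=65% or weight compliance >=143" percent, with the same upper limit for applications. SAP 4.2.3 (Table 4-1) repeats the lower limits, and SAP 4.5.1.2 makes PP, without imputation, the primary efficacy set.

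**The concern.** The new kit is in the denominator and its missed doses are deducted, but the doses applied from it are never credited. Deducting kit y misses from a total that excludes kit y has no sensible meaning. The fault is present with no missed doses at all, so it is separate from how missed doses are multiplied by days.

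At stake is membership of the primary analysis set. An adherent subject could be excluded because of a formula rather than because of behaviour. The compliance categories in SAP 4.4.1 and the good-compliance sensitivity analysis in SAP 4.5.1.3 also rest on application compliance.

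**Working it through.** **Inputs.** Seven days of treatment with four applications a day, each from its own labelled tube (Protocol 6.2), so one application per tube per day. Missed applications: none. Replacement after day d. PP requires application compliance above 80% (SAP 4.2.2, 4.2.3).

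**Reference case.** The documents give no worked figure for a replaced kit. The no-replacement branch behaves correctly here: expected 1 × 7 = 7, actual 7 − 0 = 7, so 100%.

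**Replacement branch.** The placement of brackets and of the duration term leaves several readings:

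| Reading | Expected | Actual | Compliance | Above 80%? |
|---|---|---|---|---|
| Both kits × full duration | (1 + 1) × 7 = 14 | 1 × 7 = 7 | 7/14 = 50% | No |
| Each kit over its own days, d = 1 to 5 | d + (7 − d) = 7 | d | 14.3, 28.6, 42.9, 57.1, 71.4% | No |
| Same, d = 6 | 7 | 6 | 6/7 = 85.7% | Yes |
| Literal operator order, kit x term taken as 1 | 1 + 1 × 7 = 8 | 1 | 1/8 = 12.5% | No |
| Literal operator order, kit x term taken as 7 | 8 | 7 | 7/8 = 87.5% | Yes |

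**In general.** Let X and Y be the counts for the old and new kit, each with the same meaning in both formulas. With nothing missed, compliance is X/(X + Y), which is below 100% whenever Y > 0 and exceeds 80% only if X > 4Y. Reaching 100% would require kit x to mean d applications in the denominator and 7 in the numerator. The SAP does not say that.

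**Overall percentage.** If all four tubes are replaced together, numerator and denominator are both multiplied by four and the ratio is unchanged.

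**Other durations.** The final visit is Day 8 ± 1. Counting each kit over its own days, an adherent subject fails for d ≤ 4 of 6 days (4/6 = 66.7%; 5/6 = 83.3% passes) and for d ≤ 6 of 8 days (6/8 = 75%; 7/8 = 87.5% passes).

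**With the missing term restored.** Expected d + (7 − d) = 7 and actual 7 − 0 = 7, so 100% for every d.

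**Scale for the trial.** The planned size reproduces: 2 × 22² × (1.960 + 0.842)² / (13 − 5)² gives 119 per arm against about 120 stated, and 120 per arm gives 80.4% power. The number of replaced kits is not stated. Purely as an assumed range, losing 3, 6 or 12 PP subjects per arm from 120 would lower power to 79.4%, 78.4% or 76.2%.

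**The case against.** Subtracting kit y misses shows that the kit y term was meant to be there, so this looks like a dropped term rather than a chosen rule. Protocol 12.2.4.1 defines compliance by total applications and total weight, with no restriction to one kit. Application times and tube weights are listed for each subject, and PP exclusions are discussed at the blind data review meeting, where an adherent subject showing 50% should be noticed. Replacement is probably rare: each subject receives one kit of 50 g tubes (Protocol 6.1), and each tube needs about 7 × 2 = 14 g. The primary endpoint is also analysed on mITT and ITT. All of this limits the size of the problem. It does not remove it, because neither document says that the review meeting overrides the formula.

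Three stronger conclusions are tempting and are not supported:

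- **That adherent subjects with a replaced kit will be dropped.** The readings run from 12.5% to 87.5%, and two of the cases in the table pass. Only the possibility of exclusion follows.
- **That weight compliance fails by a stated amount.** The only weight formula shown is conditional on there being no replacement. Any figure for replaced kits depends on an assumed formula, and the direction changes with the assumption. Old tube only gives 2d/14: 57.1% at d = 4 and 71.4% at d = 5, so early replacement fails the 65% limit. Old starting weight minus new final weight, with equal starting weights, gives 2(7 − d)/14: 71.4% at d = 2 and 57.1% at d = 3, so later replacement fails. The formula also sits beside a page break and has visibly lost characters, so a missing second branch may be an extraction loss.
- **That the primary result is biased or materially underpowered.** Nothing in the documents indicates how many kits were replaced or that replacement differs between arms.

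**Conclusion.** The application formula for replaced kits is wrong as written. For a subject who missed nothing over 7 days it returns 50%, d/7, or 12.5% or 87.5%, depending on the reading. Most of these fall at or below the 80% limit, so such a subject can be excluded from the primary PP set.

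This assumes one application per tube per day and replacement partway through treatment. The effect is confined to subjects with a replaced kit, whose number is unknown and probably small. No sample-size figure changes. On weight, the supportable statement is only that the available text shows no formula for these subjects.

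**What to change.** In SAP 4.4.1, for subjects with a replacement kit:

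- Expected applications from tube k: the sum over both kits of the applications scheduled on the days each kit was in use.
- Actual applications from tube k: that total minus all missed applications across both kits.

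Then check whether the full SAP contains a weight formula for replaced kits. If it does not, define gel used as the sum over both kits of dispensed weight minus last weight, with the same denominator as for subjects without a replacement. That denominator needs reconciling first: the SAP formula lines use an expected weight, whereas Protocol 12.2.4.1 and the SAP's own prose use actual applications × 2 g.

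The cost is a few lines of SAP wording and derivation code, to be settled before database lock so that no PP assignment depends on an ad hoc repair.

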## 4.5 Analysis of Efficacy

#### 4.5.1 Primary Efficacy Endpoint

#### 4.5.1.1 Primary Efficacy Endpoint Definition

The primary efficacy endpoint is change from baseline in Pain On Movement (POM) on Day 5 of treatment as assessed by a 100 mm VAS scale.

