#### 4.5.1.2 Statistical Hypothesis, Model, and Method of Analysis

The hypothesis of the study is stated below:

H0: The Diclofenac 2.32% DDEA Gel administered BID is inferior to Diclofenac1.16% DDEA gel administered QID.

 $\mu_T \text{-} \mu_S \geq \delta$ 

Where,  $\mu_S$  is the mean for a standard therapy (Diclofenac 1.16% DDEA Gel administered QID) and  $\mu$ T is the mean for test therapy (Diclofenac 2.32% DDEA Gel administered BID).  $\delta$  is the non-inferiority margin of 13 mm.

H1: Diclofenac 2.32% DDEA Gel administered BID is non-inferior to Diclofenac 1.16% DDEA gel administered QID.

 $\mu_T \text{ - } \mu_s < \delta$ 

 $\delta = 13 \text{mm}$ 

The primary efficacy analysis will be performed on PP population without imputation of missing data. The primary endpoint (Change from baseline in POM ) will be analysed using

GlaxoSmithKline Consumer Healthcare Confidential

Page **19** of **36** 

211206

Statistical Reporting and Analysis plan Draft V2.0 20JAN2021

Analysis of Covariance (ANCOVA) model with treatment and center as factors and baseline POM as covariate.

Diclofenac 2.32% DDEA Gel administered BID will be declared non-inferior to Diclofenac 1.16% DDEA gel administered QID if the upper limit of the two-sided 95% confidence interval of the difference between their mean changes from baseline VAS POM responses is less than the established margin of 13 mm.

Refer sample SAS code in APPENDIX 4.

Assumptions of normality and homogeneity of variances in the ANCOVA model will be evaluated after study un-blinding. If violations are observed then the following will be performed as a post-hoc sensitivity analysis and results will be compared with primary analysis results:

- 1. Suitable data transformations will be tried to achieve the assumptions.
- 2. If suitable transformations cannot be found, then the non-parametric Van Elteren tests will be performed using center as strata. Two sided 95% CI and p value will be presented.

POM by 100 mm VAS analogue scale (CRF page: Pain on Movement ; variable VASSCRL)will be summarized over time (**PPD**) using mITT population. Also POM by 100 mmVAS analogue scale will be summerarized over time by center using mITT population (**PPD**). Above tables (**PPD**) will be repeated for the PP population. POM by 100 mm VAS analogue scale for COVID 19 patients if any will be summarized in **PPD** using mITT population.

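### Compliance for the primary Day 5 per-protocol set is counted to the day before the final visit, so membership depends partly on doses due after the endpoint is measured

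*SAP*

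**What the plan says.** - **Endpoint.** SAP 4.5.1.1: "The primary efficacy endpoint is change from baseline in Pain On Movement (POM) on Day 5 of treatment". Protocol 4.1 puts that visit (Visit 3) at 96 ± 4 hours after the first dose.
- **Primary set.** SAP 4.5.1.2: "The primary efficacy analysis will be performed on PP population without imputation of missing data".
- **Compliance rule.** SAP 4.2.2 lists among the grounds for leaving PP: "application compliance <=80% or weight compliance <=65% or weight compliance >=143% or application compliance >=143% with study treatment". Table 4-1 in SAP 4.2.3 repeats the lower limits. Neither place gives a time window.
- **Window.** The only definition of compliance is in SAP 4.4.1: "Scheduled applications will include all scheduled applications through the day before the final visit". Expected applications are the daily number times "duration of days in the study", and gel used is computed "relative to the actual number of application made from randomization through the final visit multiplied by 2 g". Protocol 12.2.4.1 uses the same window. The further condition in SAP 4.4.1 for the DDEA 2.32% arm (good compliance on the active tubes as well as overall) specifies no other.
- **Data up to Visit 3.** SAP 4.4.1 also says that "the weight of the four tubes on Day 1, 3, 5 and 8 will be listed", and protocol 6.8 has the subject record the date and time of every application.
- **Other uses of PP.** SAP 4.5.2 and 4.6.1 use PP for the secondary endpoints, including those at Day 8.

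**The concern.** A PP set should remove departures from treatment that could distort the endpoint. A dose missed after Visit 3 cannot alter a POM value already recorded, yet it can remove that value from the primary analysis. Conversely, good compliance after Visit 3 can offset missed doses before it and keep in the set a subject who was under-dosed when the endpoint was measured.

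Two subjects with identical dosing to Day 5 can thus be classified differently because of what they did later. Membership of the set on which the non-inferiority claim rests is then conditioned partly on behaviour after the endpoint. That weakens the randomized comparison if the behaviour is related to treatment or outcome.

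**Working it through.** **The plan's own figure.** SAP 1.4 gives a margin of 13 mm, SD 22 mm, an allowed true difference of 5 mm, 80% power and a two-sided 95% CI. Then n per arm = 2 × 22² × (1.960 + 0.842)² / (13 − 5)² ≈ 119, against 120 stated, and 240 / 0.80 = 300 randomized. The figure reproduces and is not in dispute.

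**Inputs for the compliance count.**
- Four applications a day for 7 days (protocol 6.2): 4 × 7 = 28.
- Final visit on Day 8 ± 1 (protocol 4.1), counting through the day before it.
- PP requires application compliance above 80%.
- Days 1–4 give 4 × 4 = 16 applications before a 96-hour visit, or 17 with the Day 5 morning dose. This assumes four doses on Day 1.
- Compliance = applications made / applications scheduled. The SAP formula for actual applications multiplies missed doses by days; read literally it would exaggerate each miss, so the plain meaning is used here.

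**Nominal schedule, final visit on Day 8.** Above 80% of 28 means at least 23 applications (22/28 = 78.6%; 23/28 = 82.1%).

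| Subject | To Visit 3 | Whole study | In PP? |
|---|---|---|---|
| Fully dosed, stops at Visit 3, attends Visit 4 | 100% | 16/28 = 57.1% or 17/28 = 60.7% | No |
| Fully dosed, stops at end of Day 5 | 100% | 20/28 = 71.4% | No |
| Fully dosed, stops at end of Day 6 | 100% | 24/28 = 85.7% | Yes |
| Misses 3 of first 16, none later | 13/16 = 81.3% | 25/28 = 89.3% | Yes |
| Misses 4 of first 16, none later | 12/16 = 75.0% | 24/28 = 85.7% | Yes |
| Misses 5 of first 16, none later | 11/16 = 68.8% | 23/28 = 82.1% | Yes |
| Misses 6 of first 16, none later | 10/16 = 62.5% | 22/28 = 78.6% | No |

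For early misses followed by full dosing, only 4 or 5 change status between the two windows.

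**Other visit days and Day 1 counts.**
- Final visit on Day 7 (24 scheduled): stopping at Visit 3 gives 17/24 = 70.8%, removed; stopping at the end of Day 5 gives 20/24 = 83.3%, kept. Up to 4 early misses are tolerated.
- Final visit on Day 9 (32 scheduled, if not capped at 7 days): 17/32 = 53.1% and 20/32 = 62.5%, both removed. Up to 6 early misses are tolerated.
- Two doses possible on Day 1, final visit on Day 8 (26 scheduled): stopping at the end of Day 5 gives 18/26 = 69.2%, removed; 9 of 14 early doses (64.3%) with none missed later gives 21/26 = 80.8%, kept.

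**Formal early exit.** Protocol 8.2.3 carries out the Visit 4 procedures at premature termination. If that counts as the final visit, a subject who doses to the end of Day 5 and exits on Day 6 scores 20/20 = 100%. The same dosing with attendance on Day 8 scores 71.4%.

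**Weight rule (above 65%).** SAP 4.4.1 gives two denominators.
- Actual applications × 2 g: missed applications leave numerator and denominator together. Stopping at Visit 3 with full doses gives 34/34 g = 100%.
- Expected applications × 2 g = 56 g: stopping at Visit 3 gives 34/56 = 60.7%, failing; stopping at the end of Day 5 gives 40/56 = 71.4%, passing. A subject using the full 24 g on Days 5–7 needs only just over 0.65 × 56 − 24 = 12.4 g of the first 32 g (39%) to pass.

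The effect therefore runs mainly through the application rule.

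**The case against.** One PP set based on whole-treatment compliance is a common choice, and this set also serves Day 8 endpoints and the Day 5 SPID and TOTPAR, most of whose scoring period follows Visit 3. Protocol 6.7 has tubes weighed at every visit and subjects re-instructed if they use too little, which should limit late stopping. The SAP also plans the primary endpoint on mITT (4.5.1.2) and on ITT with imputation and with repeated-measures models (4.5.1.3, 4.5.3). None of these drops late stoppers, so a marked PP distortion should appear as disagreement between sets. The compliance criteria sit in a list of possible exclusions, settled at a blinded review. Finally, the PP compliance rule was already revised in SAP versions 1.0 and 2.0, and section 5 shows that observed compliance prompted the change; a further revision has a cost in credibility.

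Much of this stands. It limits the consequences but does not supply a reason to select the primary set on doses due after the endpoint. SAP 4.5.1.2 names PP as primary, Table 4-1 writes the lower limits into its definition, and a blinded review can still select on behaviour related to outcome.

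Two stronger readings are tempting. The first is that everyone who stops gel after Day 5 is removed and everyone under-dosed before it is kept. The counts above show exceptions on both sides. The second is that recovered comparator subjects stop gel and leave PP, so the estimate moves towards non-inferiority. The documents do not say why subjects stop, how many do, or whether the arms differ. If stopping depends only on recovery and recovery is equal, this mechanism shifts nothing; if the test arm recovers faster, it works against non-inferiority. Even at the SAP's 5 mm difference and 22 mm SD, assuming normality, the proportions beyond any common recovery threshold differ by at most 2Φ(5/(2 × 22)) − 1 = 9 percentage points.

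**Conclusion.** The point holds for the window: the primary Day 5 POM analysis uses a PP set whose compliance rule counts doses due after Visit 3. At the nominal schedule this removes fully dosed subjects who stop gel at Visit 3 or at the end of Day 5 but attend Visit 4. It retains subjects who miss 4 or 5 of the 16 earlier doses and none later. These results assume four doses on Day 1, a Day 8 final visit and the plain meaning of applications made over scheduled.

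No estimate of bias is offered, because neither the number affected nor its balance between arms can be derived. For scale only: at 120 per arm the SE is 22 × √(2/120) = 2.84 mm and the CI half-width 1.96 × 2.84 = 5.57 mm. At the allowed 5 mm difference the expected upper limit is 10.57 mm, 2.43 mm inside the margin.

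Severity: should-fix. The planned mITT and ITT analyses keep it below a must-fix.

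**What to change.** Before unblinding, amend SAP 4.2.2, 4.2.3 and 4.4.1 as follows.

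- For the PP set used for Day 5 POM and for Day 3 endpoints, compute application and weight compliance from the first dose to Visit 3, using the application records and the Visit 1–3 tube weights, with the existing thresholds.
- Keep the whole-study window for the descriptive compliance and exposure tables, and for the PP set used for Day 8 endpoints and Day 5 SPID and TOTPAR.
- Report Day 5 POM under the whole-study PP definition as a sensitivity analysis, so that the effect of the change is visible.

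The cost is SAP wording, one further derivation from data already collected, and two PP flags. Percentages become coarser: each missed dose counts 1/16 = 6.3 points instead of 1/28 = 3.6, so above 80% tolerates 3 misses in 16. The sample size calculation does not change.
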